7.2.2.6 Performance status

ECOG Performance status scale ([Appendix 2](#)) will be used in the timepoints as described in the [Table 7-1](#).

7.2.2.7 Laboratory evaluations

Clinical laboratory tests (hematology, clinical chemistry, viral hepatitis and pregnancy testing) will be performed at the center where the patient is enrolled (local laboratory).

All patients will have samples of blood collected on the days noted in the Visit Evaluation Schedule [Table 7-1](#). [Table 7-2](#) provides a complete list of laboratory tests that will be performed at the local laboratory.

Hepatitis B testing – At screening, HBV infection status testing will be done for HB-sAG and anti HB-c antibody. If HB-sAG is negative and anti HB-c antibody is negative, the patient can be enrolled.

If HB-sAG is positive and/or anti HB-c antibody is positive, the site will determine per local procedures if infection is active (with viral replication) or inactive (without viral replication). Possible test include, for instance, serology testing for HB-eAG and PCR for HBV DNA.

Patients with active HBV infection (with viral replication) are not eligible for enrollment.

Patients with inactive HBV infection (without viral replication) can be enrolled. Monitoring of these patients for reactivation by regular testing, using the same test is required **every 12 weeks**. Treatment in case of reactivation will be as per local procedure. This information will be collected in the eCRF.

[figure not shown]
Hepatitis C testing – At screening, HCV infection status will be assessed by the means of anti HCV antibody screen. The patient can be enrolled if anti HCV antibody is negative. If anti HCV antibody is positive then HCV RNA by PCR will be performed.

Patients with active HCV infection (with viral replication) are not eligible for enrollment.

Patients with inactive HCV infection (without viral replication) can be enrolled. Monitoring of these patients for reactivation is required by means of HCV RNA by PCR at regular intervals as per the local practice. This information will be collected in the eCRF.

Table 7-2 Local Clinical laboratory parameters collection plan

Test Category	Test Name
Hematology	Hematocrit, Hemoglobin, MCH, MCHC, MCV, Platelets, Red blood cells, White blood cells, RBC Morphology, Blasts, Differential (Basophils, Eosinophils, Lymphocytes, Monocytes, Neutrophils, Bands, Other (absolute value preferred , %s are acceptable).
Chemistry	Albumin, Alkaline phosphatase, ALT , AST , Gamma-glutamyl-transferase (GGT), Lactate dehydrogenase (LDH), Calcium, Magnesium, Phosphorus, Sodium, Potassium, Creatinine, Creatine kinase, Direct Bilirubin, Total Bilirubin, Total Cholesterol, LDL Cholesterol, HDL Cholesterol, Total Protein, Triglycerides (fasting), Blood Urea Nitrogen (BUN) or Urea, Uric Acid Amylase, Lipase, Glucose (fasting)
Viral Hepatitis	For hepatitis B: HB-sAG and anti HB-c antibody at screening. For Hepatitis C: anti HCV antibody at screening. For patients with inactive infection, testing every 12 weeks for reactivation (for HBV) and at regular intervals as per the local practice (for HCV).
Pregnancy Test	A serum pregnancy test should be performed at screening and EOT visit, while at all other timepoints, urinary pregnancy tests are sufficient.

7.2.2.8 Radiological examinations

Not applicable.

7.2.2.9 Cardiac assessments

[figure not shown]
[figure not shown]
Not applicable.

7.2.2.10 Tolerability

Not applicable

7.2.3 Pharmacokinetics

Not applicable

7.2.5 Resource utilization

Not applicable.

7.2.6 Patient reported outcomes

Patients with MF often experience significant symptoms that interfere with their quality of life (QoL) including, fatigue, early satiety, pruritus, weight loss, weakness and night sweats. The effect of ruxolitinib on patient symptoms and QoL will be measured using several assessment tools including but not limited to the MF-7, Modified MFSAF v2.0 and the Patient Global Impression of Change (PGIC). All questionnaires are patient-reported outcomes (PROs). The PRO questionnaires provided electronically (ePRO) are to be completed by the patient. The site will review for completeness.

Instructions for all PROs will be provided as separate documents. Patients must complete the questionnaire(s) before other clinical assessments at any given visit. The PRO questionnaires should be completed in the same order at each visit to ensure that the patient is answering them as consistently as possible. The questionnaires should be given in the following order:

1. MF-7
2. Separate question on Inactivity to compute Modified MFSAF v2.0
3. PGIC

Patient Reported Outcomes will be collected according to the Visit Schedule outlined in [Table 7-1](#). The patient should be given sufficient space and time to complete the PRO questionnaires.

The site personnel should check the questionnaires for completeness and ask the patient to complete any missing responses. The original questionnaire will be kept with the patient's file as the source document.

Completed questionnaire(s) and any unsolicited comments written by the patient should be reviewed and assessed by the investigator for responses which may indicate potential AEs or SAEs before any clinical study examinations. This assessment should be documented in study source records. If AEs or SAEs are confirmed, study investigators should not encourage the patient to change responses reported in the completed questionnaires. Study investigators must follow reporting instructions outlined in [Section 8](#) of the study protocol.

MF-7

The Myelofibrosis 7 Item Symptom Scale (MF-7) ([Appendix 4](#)) is a disease specific questionnaire comprised of 7 items that measures the severity of seven of the most prevalent associated symptoms including: tiredness, early satiety, abdominal discomfort, night sweats, itching (pruritus), bone pain (diffuse not joint or arthritis) and pain under ribs on left side. Each item is scored on a scale ranging from 0 (absent) to 10 (worst imaginable). The MF-7 score is computed as the sum of the observed scores in the individual items to achieve a 0-to- 70 score. There would be one recall period of 24 hours used in this questionnaire.

Modified MFSAF v2.0 – Computed through a separate Question on Inactivity

A separate question on Inactivity ([Appendix 4](#)) will measure the severity of this symptom on a scale from 0 (absent) to 10 (worst imaginable) and will allow the computation of the MFSAF v2.0 questionnaire results, as 6 out of 7 items in the latter PRO are in overlap with MF7 (they also share same 0-10 range Likert scale and ascending order, absent to worst imaginable).

PGIC

The Patient Global Impression of Change (PGIC; [Appendix 4](#)) is comprised of a single question intended to measure a patient's perspective of improvement or deterioration over time relative to treatment. The PGIC uses a seven-point scale where one (1) equals very much improved and seven (7) equals very much worse.

[figure not shown]
8 Safety monitoring and reporting

8.1 Adverse events

8.1.1 Definitions and reporting

An adverse event is defined as the appearance of (or worsening of any pre-existing) undesirable sign(s), symptom(s), or medical condition(s) that occur after patient's signed informed consent has been obtained.

Abnormal laboratory values or test results occurring after informed consent constitute adverse events only if they induce clinical signs or symptoms, are considered clinically significant, require therapy (e.g., hematologic abnormality that requires transfusion or hematological stem cell support), or require changes in study medication(s).

Adverse events that begin or worsen after informed consent should be recorded in the Adverse Events CRF. Conditions that were already present at the time of informed consent should be recorded in the Medical History page of the patient's CRF. Adverse event monitoring should be continued for at least 30 days following the last dose of study treatment. Adverse events (including lab abnormalities that constitute AEs) should be described using a diagnosis whenever possible, rather than individual underlying signs and symptoms. When a clear diagnosis cannot be identified, each sign or symptom should be reported as a separate Adverse Event.

Adverse events will be assessed and graded according to the Common Terminology Criteria for Adverse Events (CTCAE) version 4.03. Grade 1 to 5 will be used to characterize the severity of the Adverse Event.

If CTCAE grading does not exist for an adverse event, the severity of mild, moderate, severe, life-threatening, and death related to the AE corresponding respectively to Grades 1 - 5, will be used. Information about any deaths (related to an Adverse Event or not) will also be collected through a Death form.

The occurrence of adverse events should be sought by non-directive questioning of the patient during the screening process after signing informed consent and at each visit during the study. Adverse events also may be detected when they are volunteered by the patient during the screening process or between visits, or through physical examination, laboratory test, or other assessments. As far as possible, each adverse event should be evaluated to determine:

1. The severity grade (CTCAE Grade 1-5)
2. Its duration (Start and end dates)
3. Its relationship to the study treatment (Reasonable possibility that AE is related: No, Yes) or its relationship to the study treatment (Reasonable possibility that AE is related: No, Yes, investigational treatment, Yes, the study treatment (non-investigational), Yes, both and/or indistinguishable)
4. Action taken with respect to study or investigational treatment (none, dose adjusted, temporarily interrupted, permanently discontinued, unknown, not applicable)
5. Whether medication or therapy taken (no concomitant medication/non-drug therapy, concomitant medication/non-drug therapy)
6. Outcome (not recovered/not resolved, recovered/resolved, recovering/resolving, recovered/resolved with sequelae, fatal, unknown)
7. Whether it is serious, where a serious adverse event (SAE) is defined as in [Section 8.2](#).

If the event worsens the event should be reported a second time in the CRF noting the start date when the event worsens in toxicity. For grade 3 and 4 adverse events only, if improvement to a lower grade is determined a new entry for this event should be reported in the CRF noting the start date when the event improved from having been Grade 3 or Grade 4.

All adverse events should be treated appropriately. If a concomitant medication or non-drug therapy is given, this action should be recorded on the Adverse Event CRF.

Once an adverse event is detected, it should be followed until its resolution or until it is judged to be permanent, and assessment should be made at each visit (or more frequently, if

necessary) of any changes in severity, the suspected relationship to the study treatment, the interventions required to treat it, and the outcome.

All patients who have AEs, whether considered associated with the use of the investigational product or not, must be monitored to determine the outcome. The clinical course of the AE will be followed up according to accepted standards of medical practice, even after the end of the period of observation, until a satisfactory explanation is found or the investigator considers it medically justifiable to terminate follow-up. Should the AE result in death, a full pathologist's report should be supplied if and when available.

SAEs must be reported as outlined in [Section 8.2.2](#). In addition, any SAEs which occur as a result of protocol specific diagnostic procedures or interventions must also be reported.

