In the ruxolitinib-treated Phase III population, the overall frequency of AEs leading to study drug discontinuation was 11%. This frequency was similar across both studies. None of the AEs leading to discontinuation was reported in more than two patients in any group. In the ruxolitinib-treated Phase III population, the overall frequency of AEs requiring dose reduction

or interruption was 59.8%. This frequency was higher than in the control groups (placebo: 27.2%, BAT: 15.1%). The most frequently reported AEs requiring dose reduction or interruption in ruxolitinib treated patients were thrombocytopenia (36.9%), platelet count decrease (7.6%) and anemia (5.6%). The high frequency for thrombocytopenia is due to protocol-mandated dose reductions and interruptions. Although there were no protocol specified guidelines for dose reductions secondary to anemia, some investigators chose to reduce a patient's dose in the setting of anemia to minimize this particular cytopenia. The frequency of these AEs was higher than in the control groups. All other AEs requiring dose reduction or interruption occurred with a frequency of 1.3% or less in the ruxolitinib treated patients. There are no data from the use of ruxolitinib in pregnant women. Animal studies have shown that ruxolitinib is embryotoxic and foetotoxic. Teratogenicity was not observed in rats or rabbits; however, the exposure margins compared to the highest clinical dose were low and the results are therefore of limited relevance for humans. The potential risk for humans is unknown. As a precautionary measure, the use of ruxolitinib during pregnancy is contraindicated. Women of child-bearing potential should use effective contraception.

The most frequently reported adverse drug reactions were thrombocytopenia and anemia. Hematological adverse reactions (any Common Terminology Criteria for Adverse Events [CTCAE] Grade) included anemia (82.4%), thrombocytopenia (69.8%) and neutropenia (16.6%). Anemia, thrombocytopenia and neutropenia are dose related effects. The three most frequent non-hematological adverse reactions were bruising (21.6%), dizziness (15.3%) and headache (14.0%). The three most frequent non-hematological laboratory abnormalities were raised alanine aminotransferase (27.2%), raised aspartate aminotransferase (18.6%) and hypercholesterolemia (16.9%).

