Considering the typical hemoglobin level for many MF patients is already at the Grade 0/Grade 1 border (hemoglobin of 10 g/dL), assessment of a dose regimen that might provide clinically meaningful symptomatic and spleen size reduction benefits of ruxolitinib while lessening the degree of worsening hemoglobin levels is warranted.

Current label recommendation on starting doses in MF are 5, 15 or 20 mg BID, depending on platelet counts $50-100 \times 10^9/L$, $100-200 \times 10^9/L$ or $>200 \times 10^9/L$ respectively, regardless of hemoglobin level at baseline.

There is increasing literature suggesting the use of lower starting doses with up titrations depending on safety and efficacy in patients with anemia ([Tabarroki 2013](#), [Cervantes 2014](#), [Reilly 2014](#), [Harrison 2013](#), [Ho 2015](#)).

This multicenter phase II open label single arm study proposes to prospectively evaluate a starting dose of ruxolitinib 10 mg BID for 12 weeks with subsequent up titrations of 15mg BID and 20 mg BID in anemic myelofibrosis patients defined as a baseline hemoglobin < 10 g/dL (Please see [Figure 6-1](#) for details). The trial will evaluate if this alternative dosing approach achieves spleen reduction and symptom improvement to levels consistent with those reported in previous clinical trials but with an improved tolerability assessed by incidence of adverse events and transfusion requirements.

[figure not shown]
[figure not shown]

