6.3.1.1 Dose modification for hematologic toxicity

For all patients who receive ruxolitinib, there are mandatory dose decreases or dose interruptions for declining platelet counts, hemoglobin or ANC levels that might be observed while on ruxolitinib therapy. Deviations to mandatory dose interruptions and/or reductions are not allowed.

Doses may be titrated based on safety. Dosing must be held if platelet counts decline below 25,000/ μ L or if ANC that is \leq 500/ μ L or Hemoglobin is \leq 6.5 g/dL despite transfusions, while receiving ruxolitinib.

After dose interruption, when blood counts recover, dosing must be restarted at 5 mg twice daily and gradually increased based on careful monitoring of blood cell counts.

Table 6-2 Dose modifications for hematologic toxicity

[figure not shown]
The instructions provided in this table and the criteria for dose reduction / interruption are used to determine a protocol deviation.

Hematology Value at time of decline:	Dose at the time of decline				
	25 mg BID	20 mg BID	15 mg BID	10 mg BID	5 mg BID
	Dose reduction to				
Platelet < 125,000 / μ L	20 mg BID	20 mg BID	15 mg BID	10 mg BID	5 mg BID
Platelet < 100,000 / μ L	15 mg BID	15 mg BID	15 mg BID	10 mg BID	5 mg BID
Platelet < 75,000 / μ L	10 mg BID	10 mg BID	10 mg BID	10 mg BID	5 mg BID
Platelet < 50,000 / μ L	5 mg BID	5 mg BID	5 mg BID	5 mg BID	5 mg BID
Platelet < 25,000 / μ L	Treatment must be interrupted.				
Hemoglobin \leq 6.5 g/dL despite transfusions	Treatment must be interrupted.				
Absolute neutrophil count < 0.5 x 10 ⁹ /L	Treatment must be interrupted.				

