8.1.2 Laboratory test abnormalities

8.1.2.1 Definitions and reporting

Laboratory abnormalities that constitute an Adverse event in their own right (are considered clinically significant, induce clinical signs or symptoms, require concomitant therapy or require changes in study treatment), should be recorded on the Adverse Events CRF. Whenever possible, a diagnosis, rather than a symptom should be provided (e.g. anemia instead of low hemoglobin). Laboratory abnormalities that meet the criteria for Adverse Events should be followed until they have returned to normal or an adequate explanation of the abnormality is found. When an abnormal laboratory or test result corresponds to a sign/symptom of an already reported adverse event, it is not necessary to separately record the lab/test result as an additional event.

Laboratory abnormalities, that do not meet the definition of an adverse event, should not be reported as adverse events. A Grade 3 or 4 event (severe) as per CTCAE does not automatically indicate a SAE unless it meets the definition of serious as defined below and/or as per investigator's discretion. A dose hold or medication for the lab abnormality may be required by the protocol in which case the lab abnormality would still, by definition, be an adverse event and must be reported as such.

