2.8.1 Adverse events (AEs)

AE summaries will include all AEs occurring during on-treatment period. All AEs collected in the AE eCRF page will be listed along with the information collected on those AEs e.g. AE relationship to study drug, AE outcome etc. AEs starting during the post-treatment period will be flagged in the listings.

AEs will be summarized by number and percentage of subjects having at least one AE, having at least one AE in each primary system organ class (SOC) and for each preferred term (PT) using MedDRA coding. A subject with multiple occurrences of an AE will be counted only once in the respective AE category. A subject with multiple CTCAE grades for the same preferred term will be summarized under the maximum CTCAE grade recorded for the event. AE with missing CTCAE grade will be included in the 'All grades' column of the summary tables.

In AE summaries the primary system organ class will be presented alphabetically and the preferred terms will be sorted within primary SOC in descending frequency.

The following adverse event summaries will be produced by treatment; overview of adverse events and deaths (number and % of subjects who died), with any AE, any SAE, AEs by SOC and PT, summarized by relationship (all AEs and AEs related to study treatment), seriousness (SAEs and non-SAEs), leading to treatment discontinuation (drug withdrawn), leading to dose interruption/adjustment (dose increased or dose reduced), requiring additional therapy (concomitant medication or non-drug therapy) and leading to fatal outcome. In addition, a summary of serious and non-serious adverse events with number of occurrences will be produced (an occurrence is defined as >1 day between start and prior end date of record of same preferred term) as per EudraCT requirements.

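### Whether a platelet count of 50,000 to <125,000/µL is automatically an AE depends on the current dose, so platelet tolerability should be judged on laboratory grades, not AE incidence

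*Protocol*

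**What the plan says.** Protocol 8.1.1 gives four routes by which an abnormal laboratory value becomes an AE. Such values "constitute adverse events only if they induce clinical signs or symptoms, are considered clinically significant, require therapy"; the fourth route is that they "or require changes in study medication(s". Protocol 8.1.2.1 repeats the four routes and says that abnormalities outside the definition should not be reported as AEs. It adds that where the protocol itself requires a hold or medication, "the lab abnormality would still, by definition, be an adverse event and must be reported as such".

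Table 6-2 (Protocol 6.3.1.1) sets mandatory platelet-driven changes in columns headed "Dose at the time of decline". The row "Platelet < 50,000" is the first that moves the 10 mg BID column; the columns for higher doses move at higher counts. The section allows no deviation from these changes. Protocol 6.1.1 keeps patients on 10 mg BID for 12 weeks unless they meet a hold or reduction rule.

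Protocol 2.1 asks whether the regimen reaches efficacy consistent with earlier trials, but "with an improved tolerability assessed by incidence of adverse events and transfusion requirements". SAP 2.8.1 states that "AE summaries will include all AEs occurring during on-treatment period". It plans tables by relationship, seriousness and action, including AEs leading to dose interruption or adjustment, but none by dose at onset or by study period. SAP 2.8.3 separately plans platelet changes over time, worst post-baseline grade, shift tables and box plots. SAP 5.3 grades these by program from observed values.

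**The concern.** An asymptomatic count of 60,000/µL that needs no therapy and is not judged clinically significant is not an AE on 10 mg BID. The same count on 15 mg BID forces a reduction and so is one. All patients begin at 10 mg, so the AE definition is least sensitive to moderate platelet falls in the period that the low starting dose is meant to improve.

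The protocol's background shows how far dose rules can drive such a count. Section 1.2.1.2.3 reports AEs requiring dose reduction or interruption in phase III as thrombocytopenia 36.9% and anemia 5.6%, although any-grade anemia was the more frequent (82.4% against 69.8%). It explains that "The high frequency for thrombocytopenia is due to protocol-mandated dose reductions and interruptions" and that the phase III protocols had no such rule for anemia.

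At stake is the platelet part of the tolerability conclusion. The primary spleen endpoint is not affected.

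**Working it through.** The plan states no thrombocytopenia AE rate, so there is no figure to reproduce. The check reads the triggers from the table and then sizes their effect under stated assumptions.

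**Step 1. Triggers.** For each dose, take the highest platelet row of Table 6-2 whose target differs from the current dose.

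| Current dose (BID) | First forced change, platelets/µL |
|---|---|
| 25 mg | <125,000 |
| 20 mg | <100,000 |
| 15 mg | <75,000 |
| 10 mg | <50,000 |
| 5 mg | <25,000 (interruption) |

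**Step 2. Range affected.** Counts below 50,000 force a change at every dose from 10 mg up. Between 10 mg and the higher doses, ascertainment differs only for 50,000 to <75,000 (15 mg), <100,000 (20 mg) or <125,000 (25 mg). The label mild-to-moderate follows the product-information appendix, which puts grade 3 at 50,000 to 25,000 under CTCAE v3.0. The trial grades by v4.03, whose platelet bounds the documents do not print.

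**Step 3. Size if one platelet distribution applied at every dose.** Assume a log-normal nadir, so the share meeting the trigger t is F(t) = Φ[(ln t − ln median)/SD]. With median 120,000 and log-SD 0.5:
- 10 mg: Φ(−0.8755/0.5) = 4%
- 15 mg: Φ(−0.4700/0.5) = 17%
- 20 mg: Φ(−0.1823/0.5) = 36%
- 25 mg: Φ(0.0408/0.5) = 53%

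Over medians of 100,000 to 200,000 and log-SD 0.4 to 0.6, the ranges are 0-12%, 1-32%, 4-50% and 12-71%.

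If investigators report a fraction q of the unforced counts below 125,000 anyway, the reported share is F(t) + q[F(125,000) − F(t)], and the gap between two doses shrinks by the factor (1 − q). With median 100,000 and log-SD 0.4, the gap between 10 and 20 mg is 50.0 − 4.2 = 45.8 points at q = 0, 60.6 − 37.7 = 22.9 at q = 0.5, and zero at q = 1.

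**Step 4. Titration gates.** Step 3 overstates the within-trial effect, because Protocol 6.2.3 titrates to 15 mg at 100-200 ×10⁹/L and to 20 or 25 mg at ≥200 ×10⁹/L. From the lower edge of each gate, reaching the trigger takes a real fall of more than 25% at 15 mg (100 to <75), 50% at 20 mg (200 to <100) and 37.5% at 25 mg (200 to <125).

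A simulation with the 15 and 20 mg gates assumed:
- baseline log-normal with median 100, 150 or 200 ×10⁹/L and log-SD 0.6, restricted to ≥50;
- a first fall of 20-40%, with log-SD 0.3 between patients;
- a slight recovery before the gate (mean +0.1 and SD 0.2 on the log scale);
- then either no further fall or a further 20% fall.

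Everyone whose count passed a gate was titrated. The threshold effect is the share below the dose-specific trigger minus the share below 50,000. Selected scenarios, in %:

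| Baseline median, first fall | <50,000 in Weeks 1-12 | After titration, no further fall | After titration, further 20% fall |
|---|---|---|---|
| 100, 20% | 14.6 | 16.5 − 14.9 = 1.6 | 29.4 − 24.5 = 4.9 |
| 100, 40% | 30.7 | 28.8 − 27.5 = 1.3 | 43.7 − 39.8 = 3.9 |
| 150, 20% | 6.8 | 9.3 − 7.7 = 1.6 | 18.7 − 13.6 = 5.1 |
| 200, 20% | 3.3 | 5.5 − 4.2 = 1.3 | 12.2 − 7.8 = 4.4 |
| 200, 40% | 8.6 | 10.7 − 9.2 = 1.5 | 20.2 − 15.3 = 4.9 |

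Across all nine scenarios the effect is 1.3-1.6 points with no further fall and 3.9-5.1 points with a further 20% fall. In the second row the overall trigger rate falls after titration, from 30.7% to 28.8%. Dosing at 25 mg and re-escalation under Table 6-3, which has lower platelet bounds, were not modelled.

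**The case against.** The best counter-argument is that the AE count is neither the only platelet measure nor a mechanical one. Dose change is one of four routes. Clinical significance is the investigator's judgement at any dose, and Protocol 6.3.3 lets the investigator hold drug at any time for safety. That section also recommends at least weekly hematology below 100,000/µL whatever the dose, so moderate counts at 10 mg will be noticed. The gates mean that most post-titration triggers need a genuine fall. Changes in hematology parameters are already a named secondary safety endpoint, with laboratory summaries by visit, and the SAP plans no AE contrast before and after Week 12. All of this stands, and it limits the size and certainty of the problem.

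It does not remove the problem. The planned worst-grade and shift tables pool the 10 mg period with later doses. The table of AEs leading to dose change ignores dose at onset. Nothing in the SAP gives laboratory data precedence over AE incidence, which Protocol 2.1 names as a tolerability measure.

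A reader might also infer a bias against phase III trials started at 15-20 mg BID. The documents give neither the phase III AE definition nor its platelet dose-change thresholds, so that cannot be shown. The Section 1.2.1.2.3 remark concerns AEs requiring a dose change, not overall incidence. The product-information appendix bases its phase III thrombocytopenia frequencies on laboratory values.

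**Conclusion.** The point holds in limited form. AE ascertainment of platelet counts from 50,000 to <125,000/µL depends on the current dose, and its direction favours the 10 mg start. AE incidence, and especially the table of AEs leading to dose interruption or adjustment, can understate platelet toxicity at 10 mg relative to higher doses.

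The text might tempt a reader to conclude that thrombocytopenia AEs are necessarily under-counted in the first 12 weeks and must rise with titration. The documents do not support that. Other AE routes stay open, titration selects patients with higher platelets, and Protocol 1.2.1.2.3 describes thrombocytopenia as dose related, so part of any rise would be real.

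The within-trial threshold effect is about 1 to 5 percentage points. That rests on assumed platelet distributions, on the dose-change route alone and on the 15 and 20 mg gates. It shrinks towards zero as investigators report more of the unforced counts. This is an inexpensive improvement to the safety analysis, not a flaw in the design.

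**What to change.** Make three changes in SAP 2.8.1 and 2.8.3:

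1. State that conclusions on platelet tolerability rest on the programmatically graded platelet counts already planned, and that thrombocytopenia AE incidence is descriptive because its ascertainment varies with dose.
2. Add worst laboratory platelet grade separately for Weeks 1-12 and Weeks 13-24. Use scheduled and unscheduled samples, and count the Week 12 visit sample in the first period because it precedes the titration decision.
3. Tabulate thrombocytopenia AEs by dose at onset and by action taken, so that those ending in a reduction or hold can be told apart. Dose comes from the dosage administration record, and action taken is already collected under Protocol 8.1.1.

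The cost is a paragraph of SAP text and two tables from existing data. The downside is that the tolerability result may look less favourable than the AE count alone.
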